### 5.5 Handling of Missing Data

Missing data will not be imputed with the exception of incomplete medication start and stop dates and missing onset dates for AEs. Data that are excluded from the descriptive or inferential analyses will be included in the data listings. This will include those measurements from excluded subjects or measurements from unscheduled visits/collections. In calculation of the concentration summaries and displays in graphs, if values are below the limit of quantitation (BLQ) predose they will be set to zero and postdose they will be set to 'missing'; however, they will be presented as BLQ in data listings. If all concentrations at a given time point predose are BLQ, the mean will be presented as zero and the SD and CV% will be reported as not applicable.

For the calculation of PK parameters, BLQ values will be treated as follows:

- BLQ values in samples collected before administration or before the first measurable concentration will be set to zero.

- BLQ values that occur after the first measurable concentration will be set to 'missing.'
- BLQ values that occur at the end of the concentration-time profile will be set to 'missing.'

If both values of the predose average (−2 and 0 hour samples) on Day 29 are missing or BLQ, the minimum concentration for the dosing interval will be used for the calculation of AUC and associated PK parameters, as deemed appropriate. For BL-adjusted profiles, the negative values will be retained for calculation of PK parameters.

CCI

## **6 SUBJECT DISPOSITION AND BASELINE CHARACTERISTICS**

### **6.1 Subject Discontinuation**

The number of subjects who enroll in the study and the number and percentage of subjects who complete treatment and complete the study will be presented by treatment and overall for all enrolled subjects. A summary of the number of subjects within each population, along with the frequency and percentage of subjects who withdraw or discontinue from the study and the primary reason for withdrawal or discontinuation, will be summarized for each treatment and overall.

A data listing of subject disposition, including treatment and study completion status and reason for study discontinuation, will be provided. In addition, subject populations and reasons for exclusion from the population will be provided in a data listing.

### **6.2 Protocol Deviations**

Major protocol deviations will be captured as a log by the clinical research coordinator, exported into a clinical dataset, and presented in a data listing.

### **6.3 Demographics and Baseline Characteristics**

Descriptive statistics (ie, number of subjects, mean, SD, median, minimum, and maximum) will be calculated for continuous demographic and BL characteristic variables (age at Screening, weight at BL, height at Screening, and body mass index [BMI] at BL) and counts and percentages will be tabulated for categorical demographic variables (sex, race, and ethnicity) for each analysis population by treatment and overall.

A data listing will be provided for all demographic data. In addition, the BL characteristics of weight, height, and BMI will be included in the vital sign data listing.

### **6.4 Medical History**

Medical history will be displayed in a data listing. Date of diagnoses of CKD and SHPT, stage of CKD, underlying diagnosis of the CKD, and previous and concurrent diseases will be documented. Medical history data will be mapped using the Medical Dictionary for Regulatory Activities (MedDRA) Version 21.0 or higher to system organ class (SOC) and preferred term (PT) and will be listed by subject identification, medical condition reported term, onset date, and ongoing status/resolution date for all enrolled subjects and summarized by SOC and PT by treatment and overall for the safety population.

### **6.5 Inclusion and Exclusion Criteria**

Inclusion and exclusion criteria not met by randomized subjects will be provided in a data listing.

### **6.6 Substance Use**

Substance use history, including historical use of tobacco, nicotine, and alcohol, will be provided in a data listing by subject.

## 7 PHARMACOKINETIC ANALYSES

### 7.1 Serum and Plasma Concentrations

Blood samples will be collected from all subjects to determine the observed serum calcifediol **CCI** concentrations. Baseline-adjusted serum calcifediol concentrations will be calculated by subtracting the average of the BL concentrations. Negative BL-adjusted values will be retained in the analysis.

For each analyte, observed and BL-adjusted serum calcifediol **CCI** concentrations will be summarized using descriptive statistics (number of subjects, mean, SD, CV%, median, minimum, maximum, geometric mean, and geometric CV%) by visit, time point, and treatment for the PK population. Concentrations that are BLQ will be treated as outlined in Section 5.5. Mean serum and plasma concentration-time profiles will be plotted by treatment on linear (both calcifediol and paricalcitol) and semilogarithmic scales (only paricalcitol) using nominal times for the PK population. Individual concentration-time plots and spaghetti plots with subject concentration-time profiles overlaid by treatments will be included in the appendices using linear (both calcifediol and paricalcitol) and semilogarithmic scales (only paricalcitol).

Subgroups will also be presented for subjects who received the full dose of study drug versus those who received dose adjustments (ie, summaries provided for paricalcitol 1 mcg and 2 mcg on Day 29, where further categorization will be determined once the study is complete).

### 7.2 Serum and Plasma Pharmacokinetic Parameters

All PK analyses will be performed, as feasible, according to applicable standard operating procedures and protocol specifications. Pharmacokinetic parameters will be calculated using Phoenix® WinNonlin® Version 8.0 or later (Certara, Princeton, NJ, USA) and actual sampling times. If actual times are missing, nominal times may be used and will be noted in the appropriate data listing.

The PK parameters for observed and BL-adjusted serum calcifediol **CCI** will be calculated as follows (data permitting):

#### Pharmacokinetic Parameters Following the First Dose (Day 1):

*Note: The following parameters will be calculated using the data through 24 hours (once daily dosing regimens) or 28 days (monthly dosing regimens) after the first dose on Day 1 for each of the analytes, as indicated.*

$C_{\max}$ :	Maximum concentration, observed by inspection of individual study participant concentration-time profiles.
$C_{\max,0-24h}$ :	Maximum concentration over a 24-hour interval, observed by inspection of individual study participant concentration-time profiles. Presented for the monthly dosing regimens only. (For the daily dosing regimens, $C_{\max}$ will be equivalent to $C_{\max,0-24h}$ .)

$T_{\max}$ :	Time of maximum concentration, obtained directly from the observed concentration-time data.
$T_{\max,0-24h}$ :	Time of maximum concentration over a 24-hour interval, obtained directly from the observed concentration-time data. Presented for the monthly dosing regimens only. (For the daily dosing regimens, $T_{\max}$ will be equivalent to $T_{\max,0-24h}$ .)
$AUC_{0-t}$ :	AUC from time 0 to the last measurable time point, calculated by linear-log trapezoidal summation.
$AUC_{0-t'}$ :	AUC from time 0 to a fixed time point $t'$ , calculated by linear-log trapezoidal summation. This will include the AUC from time 0 to 24 hours ( $AUC_{0-24h}$ ) for all dosing regimens and AUC from time 0 to 28 days ( $AUC_{0-28d}$ ) for the monthly dosing regimens only.
$AUC_{0-\infty}$ :	AUC from time 0 extrapolated to infinity, calculated as $AUC_{0-t} + C_{\text{last}}/\lambda_z$ , where $C_{\text{last}}$ is the last measurable concentration (paricalcitol only).  The reliability of $AUC_{0-\infty}$ values is contingent upon the percentage obtained by extrapolation ( $AUC_{\text{ext}}$ ), where $AUC_{\text{ext}}$ is $>40\%$ , $AUC_{0-\infty}$ values are considered unreliable.
$AUC_{\text{ext}}$ :	Percentage of $AUC_{0-\infty}$ obtained by extrapolation, calculated as $[(AUC_{0-\infty} - AUC_{0-t})/AUC_{0-\infty}] \times 100$ ; (a diagnostic parameter calculated and listed in the data listing, but not included in the descriptive statistics; paricalcitol only).
$\lambda_z$ :	Terminal elimination rate constant (if estimable), determined by linear regression of the terminal points of the log-linear concentration-time profile (paricalcitol only).  Calculation of $\lambda_z$ requires a minimum of 3 data points after (and not including) $C_{\text{max}}$ . The adjusted coefficient of determination ( $R^2\text{-adj}$ ) for the linear regression must be at least 0.80.
$t_{1/2}$ :	Terminal elimination half-life (if estimable), determined as $[\ln(2)/\lambda_z]$ (paricalcitol only).
$CL/F$ :	Apparent clearance after extravascular administration, calculated as $\text{Dose}/AUC_{0-\infty}$ (paricalcitol only).
$V_d/F$ :	Apparent volume of distribution after extravascular administration, calculated as $\text{Dose}/(\lambda_z \times AUC_{0-\infty})$ (paricalcitol only).
$T_{\text{ss}}$ :	Predicted time to steady state, calculated as $(t_{1/2} \times 5)$ (paricalcitol only).

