#### 2.2.2 Pharmacokinetic Endpoints

The following PK parameters will be calculated for observed and baseline (BL)-adjusted serum calcifediol (also known as 25-hydroxyvitamin D3 [25D3]) **CCI** concentrations using noncompartmental methods (data permitting), where additional parameters may be evaluated based on the concentration-time data:

1.  $C_{\max}$  – maximum concentration (including  $C_{\max}$  during a 24-hour interval [ $C_{\max,0-24h}$ ]);
2.  $T_{\max}$  – time of maximum concentration (including  $T_{\max}$  during a 24-hour interval [ $T_{\max,0-24h}$ ]);
3.  $AUC_{0-t}$  – area under the concentration-time curve (AUC) from time 0 to the last measurable time point;
4.  $AUC_{0-t}$  – AUC from time 0 to a fixed time point t. This will include the AUC from time 0 to 24 hours ( $AUC_{0-24h}$ ) for all dosing regimens and AUC from time 0 to 28 days ( $AUC_{0-28d}$ ) for the monthly dosing regimens only;
5.  $AUC_{0-56d}$  – AUC over the entire study period (56 days);
6.  $AUC_{\tau}$  – AUC during the dosing interval ( $\tau$ ), where  $\tau$  = 24 hours for the daily dosing regimens and  $\tau$  = 28 days for the monthly dosing regimens.  $AUC_{\tau}$  will only be calculated for the monthly dosing regimens if deemed appropriate;
7.  $AUC_{0-\infty}$  – AUC from time 0 extrapolated to infinity (paricalcitol only);
8.  $AUC_{\text{ext}}$  – percentage of  $AUC_{0-\infty}$  obtained by extrapolation (a diagnostic parameter calculated and listed in the data listing, but not included in the descriptive statistics) (paricalcitol only);
9.  $C_{\text{avg}}$  – average concentration over a dosing interval after multiple doses. For the monthly dosing regimens, average exposure may be calculated over a 24-hour interval ( $C_{\text{avg},24h} = AUC_{0-24h}/24$  hours), the entire dosing interval ( $C_{\text{avg},28d} = AUC_{0-28d}/28$  days), and/or over the entire study period ( $C_{\text{avg},56d} = AUC_{0-56d}/56$  days);

10.  $T_{ss}$  – predicted time to steady state (paricalcitol only);
11.  $\lambda_z$  – terminal elimination rate constant (paricalcitol only);
12.  $t_{1/2}$  – terminal elimination half-life (paricalcitol only);
13.  $CL/F$  – apparent clearance after extravascular administration (paricalcitol only);
14.  $CL_{ss}/F$  – apparent clearance after multiple extravascular administrations;
15.  $V_d/F$  – apparent volume of distribution after extravascular administration (paricalcitol only);

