**Pharmacokinetic Parameters Following the Last Dose (Day 29):**

*Note: The following parameters will be calculated using the data through 24 hours for the once daily dosing regimens or through the EOS/ET sample on Day 57 (ie, 28 days post Day 29 dose) for the monthly dosing regimens, where possible.*

$C_{max}$ :	Maximum concentration during the dosing interval (24 hours for once daily and 28 days for monthly), observed by inspection of individual study participant concentration-time profiles.
$C_{max,0-24h}$ :	Maximum concentration over a 24-hour interval, observed by inspection of individual study participant concentration-time profiles. Presented for the monthly dosing regimens only. (For the daily dosing regimens, $C_{max}$ will be equivalent to $C_{max,0-24h}$ .)
$T_{max}$ :	Time of maximum concentration during the dosing interval (24 hours for once daily and 28 days for monthly), obtained directly from the observed concentration-time data.
$T_{max,0-24h}$ :	Time of maximum concentration over a 24-hour interval, obtained directly from the observed concentration-time data. Presented for the monthly dosing regimens only. (For the daily dosing regimens, $T_{max}$ will be equivalent to $T_{max,0-24h}$ .)
$AUC_{0-t}$ :	AUC from time 0 to the last measurable time point, calculated by linear-log trapezoidal summation.
$AUC_{\tau}$ :	AUC during the dosing interval ( $\tau$ ), where $\tau = 24$ hours for the daily dosing regimens and $\tau = 28$ days for the monthly dosing regimens.
$AUC_{0-t'}$ :	AUC from time 0 to a fixed time point $t$ , calculated by linear-log trapezoidal summation. This will include the $AUC_{0-24h}$ for the monthly dosing regimens (equivalent to $AUC_{\tau}$ for the daily dosing regimens).
$C_{avg}$ :	Average concentration over a dosing interval after multiple doses, calculated as $AUC_{\tau}/\tau$ . For the monthly dosing regimens, average exposure over a 24-hour interval ( $C_{avg,24h} = AUC_{0-24h}/24$ hours) and/or over the entire dosing interval ( $C_{avg,28d} = AUC_{0-28d}/28$ days).
$RA,C_{max}$	Accumulation ratio based on $C_{max}$ , calculated as $(C_{max}, \text{Day 29})/(C_{max}, \text{Day 1})$ .
$RA,AUC$	Accumulation ratio based on AUC. For once daily dosing regimens, calculated as $(AUC_{\tau}, \text{Day 29})/(AUC_{0-24h}, \text{Day 1})$ . For monthly dosing regimens, AUCs from 0 to 24 hours or 28 days may be used, as deemed appropriate.

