LF	Linearity factor, calculated as $(AUC_{\tau}, \text{Day 29})/(AUC_{0-\infty}, \text{Day 1})$ (paricalcitol only).

$\lambda_z$ :	Terminal elimination rate constant (if estimable), determined by linear regression of the terminal points of the log-linear concentration-time profile (paricalcitol only).  Calculation of $\lambda_z$ requires a minimum of 3 data points after (and not including) $C_{max}$ . The $R^2$ -adj for the linear regression must be at least 0.80.
$t_{1/2}$ :	Terminal elimination half-life (if estimable), determined as $[\ln(2)/\lambda_z]$ (paricalcitol only).
$CL_{ss}/F$ :	Apparent clearance after multiple extravascular administrations, calculated as Dose/ $AUC_{tau}$ (calculated for paricalcitol and for BL-adjusted calcifediol following the calcifediol treatments only, where possible).

In addition to the above parameters, measures of exposure over the entire 56-day study period will be determined for calcifediol (for the monthly dosing regimens only), according to the following calculations:

- $AUC_{0-56d}$ : AUC over the entire study period (56 days), calculated as  $(AUC_{0-28d}, \text{Day 1}) + (AUC_{tau}, \text{Day 29})$ ;
- $C_{avg,56d}$ : Average concentration over the entire study period (56 days), calculated as  $AUC_{0-56d}/56$  days.

All subjects in the PK population will be included in the descriptive statistics for the PK parameters. No value for  $\lambda_z$ ,  $AUC_{0-inf}$ ,  $AUC_{ext}$ ,  $CL/F$ ,  $V_d/F$ ,  $T_{ss}$ , or  $t_{1/2}$  will be reported for cases that do not exhibit a terminal log-linear phase in the concentration-time profile. No PK parameters will be calculated for subjects with insufficient data following BLQ imputation, see Section 5.5 (eg, fewer than 3 quantifiable postdose concentrations for AUC,  $\lambda_z$ , and associated parameters;  $C_{max}$  and  $T_{max}$  parameters may be presented for subjects with fewer quantifiable concentrations, if deemed appropriate).

Descriptive statistics of PK parameters for calcifediol and paracalcitol will be provided for the PK population by visit and treatment and will include number of subjects, mean, SD, CV%, median, minimum, maximum, geometric mean and geometric CV%.

Subgroups will also be presented for subjects who received the full dose of study drug versus those who received dose adjustments (ie, summaries provided for paricalcitol 1 mcg and 2 mcg on Day 29, where categories will be determined once the study is complete).

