### 7.3 Statistical Analysis of Pharmacokinetic Parameters

As an exploratory analysis, PK parameters for observed and BL-adjusted serum calcifediol will be compared between treatments using a mixed-effects model for the PK population. The dependent variable will be the value of the PK parameter. The model will include a term for treatment and BL calcifediol as a covariate. The PK parameters

compared may include  $C_{max}$  and  $AUC_{0-24h}$  for Day 1 and  $C_{max}$ ,  $AUC_{0-24h}$  (ie,  $AUC_{tau}$  for daily dosing regimen), and  $C_{avg}$  for Day 29. Additional parameters (eg, alternative  $AUC_{0-t}$  parameters) may be compared (and/or substituted) as deemed appropriate.

[figure not shown]
Treatment least-squares means and least-squares differences and 95% confidence intervals for the difference will be constructed for the values of each parameter. In addition, the  $P$  values will be presented for treatment and BL in the analysis table.

The SAS Proc Mixed code is as follows:

[figure not shown]
```
PROC MIXED DATA = adpc;
  BY paramn paramcd param;
  CLASS trtp;
  MODEL aval = trtp base_calcifediol;
  ESTIMATE 'CTAP101 Capsules vs. Calcifediol IR' trtp 1 -1 0 0 / cl;
  ESTIMATE 'CTAP101 Capsules vs. Cholecalciferol' trtp 1 0 -1 0 / cl;
  ESTIMATE 'CTAP101 Capsules vs. Paracalcitol plus cholecalciferol' trtp 1 0 0 -1 / cl;
  RUN;
```

[figure not shown]
Alternative statistical analyses may be provided if insufficient data or issues with the model are found.

CCI

CCI

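### The exploratory calcifediol model in SAP 7.3 compares Cmax and Cavg taken over 24 hours in the daily arms with the same-named values taken over 28 days in the monthly arms

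*SAP*

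**What the plan says.** SAP 7.2 sets the window by regimen. The Day 1 parameters "will be calculated using the data through 24 hours (once daily dosing regimens) or 28 days (monthly dosing regimens) after the first dose". Day 29 Cmax is "Maximum concentration during the dosing interval (24 hours for once daily and 28 days for monthly), observed by inspection" of each subject's profile. Day 29 Cavg is "Average concentration over a dosing interval after multiple doses, calculated as" AUCtau divided by tau, with tau equal to 24 hours in the daily arms and 28 days in the monthly arms.

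For Cavg there is a second route. SAP 2.2.2 states: "For the monthly dosing regimens, average exposure may be calculated over a 24-hour interval", over the whole dosing interval, or over the study period. The Day 29 list in SAP 7.2 likewise allows the 24-hour version, the 28-day version or both.

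SAP 7.2 also derives Cmax,0-24h for the monthly arms and notes that plain Cmax is the same quantity in the daily arms.

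SAP 7.3 then states: "As an exploratory analysis, PK parameters for observed and BL-adjusted serum calcifediol will be compared between treatments". The candidate list is Cmax and AUC0-24h for Day 1, and Cmax, AUC0-24h and Cavg for Day 29. Further parameters may be added or swapped in. The model has treatment and baseline calcifediol as terms and estimates CTAP101 against each other arm, with 95% confidence intervals and P values. On scale: "The dependent variable will be the value of the PK parameter"; no log transformation is visible.

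**The concern.** One variable name in the model carries two definitions, and the definition is fixed by treatment arm. The baseline covariate cannot separate a treatment effect from a window effect that coincides with it. For CTAP101 against high-dose cholecalciferol, the planned Cmax difference sets the highest value in one day against the highest value in four weeks.

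SAP 7.3 uses a common 24-hour window for AUC, but names plain Cmax rather than the 24-hour Cmax that SAP 7.2 already provides. For Day 29 Cavg the window in the monthly arms is not stated, so it could be settled after the concentrations of an open-label study have been seen.

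What is at stake is how the reported differences, intervals and P values are read. Comparing the arms is among the principal aims in Protocol 3.2, so they are likely to be read.

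**Working it through.** The documents state no figure for this comparison, so there is nothing to reproduce. The check counts the affected contrasts and then sizes the window effect.

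**1. Which contrasts are matched**

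| Parameter in SAP 7.3 | CTAP101 vs IR calcifediol | CTAP101 vs cholecalciferol 300,000 IU | CTAP101 vs paricalcitol + 800 IU |
|---|---|---|---|
| Day 1 Cmax | 24 h vs 28 d | 24 h vs 28 d | matched |
| Day 1 AUC0-24h | matched | matched | matched |
| Day 29 Cmax | 24 h vs 28 d | 24 h vs 28 d | matched |
| Day 29 AUC0-24h | matched | matched | matched |
| Day 29 Cavg | 24 h vs 28 d by default, otherwise open | same | matched |

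That is 5 × 3 = 15 contrasts per scale (observed or baseline-adjusted), of which 3 × 2 = 6 are unmatched by the default definitions.

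**2. Inputs**
- Cholecalciferol: calcifediol peak at about 7 days, half-life about 50 days (Protocol Appendix 4, section 5.2). This is the 800 IU product text; applying it to 300,000 IU is an assumption, so the peak is varied over 5-10 days.
- IR calcifediol: peak at about 4 hours, half-life 18-21 days (Protocol Appendix 2, section 5.2).
- CTAP101: half-life about 30 days, steady state reached after 12 weeks (Protocol 3.2).
- Sampling: 0, 2, 4, 6, 12, 24 and 48 hours, then weekly, after the Day 1 and Day 29 doses.

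**3. Model.** One compartment, baseline-adjusted, equal bioavailability for both doses: f(t) = ka/(ka − ke) × (exp(−ke·t) − exp(−ka·t)), with ke = ln 2/half-life and ka solved from the peak time. The Day 1 profile is f(t) and the Day 29 profile is f(t) + f(t + 28).

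**4. Cholecalciferol Cmax** (ke = ln 2/50, ka = 0.536 per day)
- Day 1: 24-hour maximum 0.412, 28-day maximum 0.908; ratio 0.908/0.412 = 2.20 (1.6-3.1 for a peak at 5-10 days).
- Day 29: 1.099 and 1.539; ratio 1.40 (1.2-1.5).
- With an assumed half-life of 30 days and the peak at 7 days, the ratios are 2.39 and 1.48, so the result does not hinge on the 50 days.

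**5. IR calcifediol Cmax.** The peak falls inside the first day, so the 28-day/24-hour ratio is 1.00 on both days.

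**6. Day 29 Cavg, 28-day over 24-hour window**
- IR: 0.820/1.292 = 0.635 (half-life 18 days) and 0.911/1.352 = 0.674 (21 days), that is −37% to −33%.
- Cholecalciferol: 1.359/0.916 = 1.48, that is +48% (+36% to +57% for a peak at 5-10 days).

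**7. CTAP101, fraction of steady state 1 − exp(−k·t), k = ln 2/30**
- After the first dose: 0.023 at 24 hours against 0.476 at 28 days; ratio 0.05.
- After the Day 29 dose: 0.488 at the end of Day 29 against 0.726 at Day 57; ratio 0.67.
- Mean over Day 29 is 0.482 and over Day 29-57 is 0.614; ratio 0.79.

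**8. Redundancy.** Cavg,24h = AUC0-24h/24, so modelling it on Day 29 repeats a row already in the list.

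The ratios and percentages apply to baseline-adjusted values; on the observed scale they are closer to 1. Because the model works on raw differences, the window effect enters a contrast as the same number of ng/mL on either scale.

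**The case against.** Several counter-arguments have force. Cmax and Cavg per dosing interval are legitimate definitions when regimens with different intervals are compared. The analysis is exploratory, its parameter list is only a set of candidates, and substitution is allowed. SAP 7.2 already gives Cmax,0-24h for the monthly arms, so the descriptive parameter tables will show a matched 24-hour maximum, and SAP 7.1 summarises concentrations by visit in all arms. A late cholecalciferol peak would be visible.

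The interval argument is stronger at steady state, but Protocol 3.2 puts CTAP101 steady state at 12 weeks, so neither Day 1 nor Day 29 qualifies. The substitution wording permits a repair without prescribing one. The descriptive tables help a careful reader but do not change the modelled contrast.

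The objection also limits the point:
- A reader might infer that the IR calcifediol Cmax contrast is sound, or equally that it is distorted. Neither holds without naming a reference window. It is unchanged under 24-hour matching, but would change under 28-day matching because the CTAP101 value would change.
- A reader might want the effect in ng/mL. The documents give no calcifediol peak for 300,000 IU, so only ratios can be supported.
- A reader might see a further error in the 56-day measures, because SAP 2.2.2 lists "AUC over the entire study period (56 days") with no regimen limit while SAP 7.2 says "measures of exposure over the entire 56-day study period will be determined for calcifediol (for the monthly dosing regimens only"). That is a general list against a specific rule. In the monthly arms the SAP 7.2 formula is correct, since AUCtau there covers 28 days.

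**Conclusion.** The point holds for Cmax on Days 1 and 29 and for Cavg on Day 29, in the contrasts of CTAP101 with the two monthly arms. As written, those contrasts compare different windows, and the monthly Cavg window is not fixed.

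The size depends on the arm. The plan roughly doubles cholecalciferol's Day 1 Cmax relative to a 24-hour window and raises its Day 29 Cmax by about 40%. IR Cmax is the same in either window. The Cavg choice moves IR calcifediol and cholecalciferol in opposite directions, so no single correction can be applied afterwards. These figures rest on a one-compartment model, equal bioavailability at both doses, and the 800 IU product's peak time carried over to 300,000 IU.

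A reader might infer that the whole model is invalid or that a study conclusion is at risk. The documents do not support that. Nine of the 15 contrasts per scale are matched, the study is descriptive with no primary or secondary efficacy endpoint, and the model is labelled exploratory. The case for changing the SAP is that the repair is small and should be written down rather than left to later choice.

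**What to change.** In SAP 7.3:
1. Replace Cmax by Cmax,0-24h for Days 1 and 29. State that for cholecalciferol this is early exposure and not the peak (in the illustration, 0.412/0.908 = 45% of it on Day 1). Report the 28-day Cmax of the monthly arms descriptively.
2. Define the modelled Day 29 Cavg as the average over Day 29-57 in all four arms, from the weekly samples already scheduled. Do not model Cavg,24h.
3. Optionally, derive AUC0-28d (Day 1-29) in all arms for a matched first-month comparison. Do not also model AUC0-56d: with the average in item 2 taken per day, it equals AUC0-28d + 28 × Cavg over Day 29-57, so in the same subjects its contrasts are fixed by the other two.

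Keep these contrasts labelled exploratory.

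The cost is SAP wording and a little extra noncompartmental output, with no new samples or visits. Items 1 and 2 leave the list at 5 parameters and 15 contrasts per scale; item 3 makes it 6 × 3 = 18, with three more unadjusted P values. Long-window values in the daily arms rest on weekly samples and are affected by dose changes. Sparse sampling itself matters little: in a noise-free CTAP101 check with the scheduled times and bedtime dosing (absorption peak at 4 or 12 hours, assumed baseline 15 or 25 ng/mL), the linear-log trapezoid was within 0.5% of the true AUC for Day 29-57 and within 0.9% for Day 1-29. Dose changes are the larger difficulty, so these contrasts should be read with the dose-adjustment subgroups that SAP 7.2 already plans.

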5.2 Pharmacokinetic properties

Vitamin D

Sun exposure: UVB light converts 7-dehydrocholesterol, found in the skin, to colecalciferol.

Absorption: Vitamin D is easily absorbed in the small intestine. Food intake potentially increases the absorption of vitamin D.

Distribution and biotransformation: Colecalciferol and its metabolites circulate in the blood bound to a specific globulin. Colecalciferol is converted in the liver by hydroxylation to 25-hydroxycholecalciferol. It is then further converted in the kidneys to 1,25-dihydroxycholecalciferol. 1,25-dihydroxycholecalciferol is the active metabolite responsible for increasing calcium absorption. Vitamin D, which is not metabolised, is stored in adipose and muscle tissues.

After a single oral dose of colecalciferol, the maximum serum concentrations of the primary storage form are reached after approximately 7 days. 25(OH)D₃ is then slowly eliminated with an apparent half-life in serum of about 50 days. Colecalciferol and its metabolites are excreted mainly in the bile and faeces.

Elimination: Vitamin D is excreted mainly in bile and faeces with a small percentage found in urine.

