### 5.4 Pharmacokinetic Population

The PK population will include all subjects who are randomly assigned to treatment, receive at least 1 dose of study drug, have no major protocol deviations, have at least 1 PK data point at BL, and sufficient measureable serum calcifediol or paricalcitol concentrations to facilitate the calculation of at least 1 postdose PK parameter using validated methods. Presentation of data will use the actual treatment. In cases where a subject's dosing compliance is found to be an issue, PK parameters may not be calculated for that subject.

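### In the two monthly arms, calcifediol AUC0-t stops at each subject's last sample, so anyone leaving part-way through a 28-day window is summarised with a partial area beside full ones

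*SAP*

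**What the plan says.** SAP 7.2 defines AUC0-t identically after the Day 1 and Day 29 doses: "AUC from time 0 to the last measurable time point, calculated by linear-log trapezoidal summation". The data window depends on the regimen. The Day 1 note reads "The following parameters will be calculated using the data through 24 hours (once daily dosing regimens) or 28 days (monthly dosing regimens"; after Day 29 the monthly arms run "through the EOS/ET sample on Day 57", where possible. The Day 29 Cmax is the "Maximum concentration during the dosing interval (24 hours for once daily and 28 days for monthly".

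Three provisions decide who is tabulated:

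- SAP 5.4 admits a subject without major deviations who has a baseline PK value and enough data "to facilitate the calculation of at least 1 postdose PK parameter using validated methods".
- SAP 7.2 states: "All subjects in the PK population will be included in the descriptive statistics for the PK parameters".
- The only data floor in SAP 7.2 is an example of insufficient data: "fewer than 3 quantifiable postdose concentrations for AUC". It allows fewer for Cmax and Tmax.

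SAP 5.5 does not impute missing concentrations. Protocol 6.4.2 says missed samples should not be redrawn, except for safety, and Protocol 6.8 plans no replacement of subjects.

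Fixed-window measures are also planned: AUC0-24h, AUC0-28d, AUCtau, AUC0-56d and the averages derived from them. The SAP does not say whether the 28-day and 56-day measures are left missing when a window is incomplete.

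**The concern.** A last-measurable-point area suits a drug that falls below the assay limit. Calcifediol circulates at baseline, so that endpoint is simply the date of the last sample. In a 28-day window, AUC0-t then reflects length of follow-up as well as exposure: a subject last seen on Day 15 supplies a 14-day area to the same table row as 28-day completers. This generally lowers the arm's mean and geometric mean and inflates its CV. If leaving differs between the two monthly arms, which share the window, it produces a difference between them that is not pharmacokinetic. The daily arms use a 24-hour window and are hardly touched.

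The SAP guards against unreliable areas for paricalcitol, with a 40% limit on extrapolated area and a fit criterion for the terminal slope. Calcifediol has no counterpart.

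Cmax raises a narrower version of the problem. Protocol Appendix 4, section 5.2, says that after a single oral cholecalciferol dose "the maximum serum concentrations of the primary storage form are reached after approximately 7 days". A cholecalciferol subject last sampled before then has a pre-peak Cmax.

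**Working it through.** The plan gives no dropout rate, expected AUC or sample size calculation, so it has no figure to reproduce. The check is an illustration for the first dose; the second window was not calculated separately.

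**Inputs from the documents.**
- IR calcifediol: peak at about 4 h, half-life 18-21 days (Protocol Appendix 2, 5.2).
- Cholecalciferol: 25D3 peak at about 7 days, apparent half-life about 50 days (Protocol Appendix 4, 5.2, the 800 IU product information).
- Sampling at 0, 2, 4, 6, 12, 24 and 48 h, then weekly. About 20 subjects per arm.

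**Assumptions.** Baseline B of 10-25 ng/mL; peak rise R of 10-60 ng/mL; one-compartment profiles identical across subjects; 1 to 4 of 20 leaving within the window considered.

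**Step 1: share of the 28-day area, IR calcifediol.** Ignoring the short absorption phase, with half-life h:

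A(T) = B·T + R·(1 − 2^(−T/h))·h/ln 2, and share = A(T)/A(28).

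Example with B = 20, R = 20, h = 21:
- A(7) = 140 + 20 × 0.2063 × 30.30 = 265.0
- A(28) = 560 + 20 × 0.6031 × 30.30 = 925.5
- share = 265.0/925.5 = 28.6%

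**Step 2: all inputs.** The ranges below use the planned sampling times and a linear-up, log-down trapezoid, over observed and baseline-adjusted values.

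| Last sample | IR calcifediol | High-dose cholecalciferol |
|---|---|---|
| 7 d | 27-36% | 22-24% |
| 14 d | 52-63% | 50% |
| 21 d | 77-84% | 75-76% |

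**Step 3: effect on the arm summary.** With k leavers of 20, each keeping share f:
- arithmetic mean changes by −(k/20)(1 − f)
- geometric mean changes by f^(k/20) − 1
- CV = √[1.0625 × E(f²)/E(f)² − 1], assuming a completer CV of 25%, so that 1.0625 = 1 + 0.25². Here E(f) = 1 − k/20 + (k/20)f, and E(f²) has the same form with f².

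| f | k | Mean | Geometric mean | CV |
|---|---|---|---|---|
| 0.25 (about 7 d) | 1 | −3.8% | −6.7% | 31% |
| 0.25 | 4 | −15.0% | −24.2% | 44% |
| 0.50 (about 14 d) | 1 | −2.5% | −3.4% | 28% |
| 0.50 | 4 | −10.0% | −12.9% | 34% |
| 0.75 (about 21 d) | 1 | −1.2% | −1.4% | 26% |
| 0.75 | 4 | −5.0% | −5.6% | 27% |

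For example, 0.25^(1/20) = 0.933 and 0.25^(4/20) = 0.758. At the extreme, the 2, 4 and 6 h samples alone satisfy the three-concentration example. The share is then about 1% for IR calcifediol, and one such subject lowers the geometric mean by 1 − 0.01^(1/20) = 21%.

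**Step 4: Day 1 Cmax.**
- IR calcifediol: the peak at about 4 h is captured by any follow-up to 6 h, so 100% is kept.
- Cholecalciferol: take c(t) proportional to e^(−ke·t) − e^(−ka·t), with ke = ln 2/50 = 0.0139 per day. Solving ln(ka/ke)/(ka − ke) = 7 gives ka = 0.536 per day. At 48 h the rise is (0.973 − 0.342)/(0.908 − 0.023) = 0.71 of its peak.
- That is the baseline-adjusted share. The observed share is (B + 0.713R)/(B + R): 83% for B = 20, R = 30, and 92% for B = 25, R = 10. From 7 days on it is 100%.

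**The case against.** The strongest answer is that AUC0-t is a supplementary parameter whose name discloses what it is. The fixed-window measures that matter are already planned, the study is descriptive, and the tables show n, minimum and maximum with individual values listed. The SAP also calculates only where data allow, excludes major protocol deviations and may withhold parameters for poor compliance. An early-termination visit collects a further calcifediol sample.

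Much of this stands, and it limits the point. It does not remove it. The discretionary phrases set no rule, and early withdrawal is not among the examples of major deviations in Protocol 10.8. An early-termination sample lengthens a partial window without completing it. For calcifediol the SAP confines the terminal slope to paricalcitol, so it provides no extrapolation, yet it does not say that an incomplete AUC0-28d or AUCtau is left missing.

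The dropout objection also has force. Leavers before Day 29 have no Day 29 parameters, and leavers after it do not truncate the Day 1 area. A given total dropout is therefore split between windows, and the 1 to 4 of 20 must be read as leavers within one window.

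A reader might infer that Cmax is truncated in both monthly arms, or that the between-arm comparison with CTAP101 rests on truncated areas. The documents support neither:
- The IR calcifediol peak at about 4 h protects that arm's Cmax.
- The SAP 7.3 model names Cmax and AUC0-24h for Day 1, and those plus Cavg for Day 29. AUC0-t could enter only through the clause allowing other parameters to be added or substituted.
- AUC0-24h does not change when a subject leaves after 24 h.
- AUC0-t spans 24 h in the daily arms, so it was never a like-for-like comparison with CTAP101.

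**Conclusion.** The point holds for calcifediol AUC0-t in the IR calcifediol and high-dose cholecalciferol arms, in both dosing windows. Followed as written, the SAP mixes partial areas with 28-day areas in one row. For 1 to 4 leavers of 20 within the first window, the geometric mean is lowered by about 7-24% if they leave near 7 days and 1-6% if they leave near 21 days. These sizes rest on assumed dropout, baselines and rises, and on identical one-compartment profiles.

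The shift is generally downward, not always: SAP 5.5 retains negative baseline-adjusted values, so truncation could raise the adjusted area of a profile that falls below baseline.

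For Cmax the exposure is confined to high-dose cholecalciferol subjects last sampled before about 7 days post-dose. It matters because Cmax is named in the SAP 7.3 model. The 7-day peak comes from the 800 IU product information; the 50,000 IU product information gives no peak time.

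This is a tabulation rule to settle before database lock, because under SAP sections 1 and 4 an exclusion designed afterwards would be post hoc. It does not undermine the exploratory comparison as a whole.

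**What to change.** Add to SAP 7.2, with a cross-reference in 7.3:

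1. Keep calcifediol AUC0-t for every subject in the listing, since Protocol Table 4 specifies it.
2. In the monthly arms, summarise AUC0-t, AUC0-28d, AUCtau, and the Cavg,28d and 56-day measures derived from them, only for subjects sampled to the end of the relevant 28-day window: the Day 29 predose sample for the first dose and the Day 57 sample for the second.
3. In the cholecalciferol arm, summarise and model 28-day Cmax and Tmax only for subjects with a sample at or after about 7 days following that dose. Apply no such restriction to IR calcifediol.
4. Flag the remaining values in the listing, and print the number used and the number excluded beside each parameter.

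Deleting AUC0-t altogether would depart from Protocol Table 4, and a later Cmax cut-off such as 14 days would discard valid peaks in both arms.

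The cost is a few lines of SAP text and no new data. With 1 to 4 leavers, 19 to 16 of 20 subjects remain in the 28-day rows, and under identical profiles the truncation shift is zero. The downside is that a few early leavers appear only in the listing. If leaving is related to exposure, restricting to completed windows does not remove that selection, and the report should say so.
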